5.0 Procedures Involved

5.1

Aim 1. Understand and prioritize key stakeholder goals, challenges, affordances, and constraints

Aim 1 of this study will use an exploratory sequential (qual→quant) mixed-methods design to conduct semi-structured focus groups (qual) with mental health patients, providers, and administrators and a survey (quant) with providers. We will conduct 4 focus groups per stakeholder group (patient, provider, administrator) and each focus group session will include up to 6 participants. Half of the focus groups will consist of stakeholders from public healthcare institutions and the other half will consist of stakeholders from private healthcare institutions. We then will enroll 100 providers to complete the survey. Analyses will inform the design of new Adhere.ly features and exercises and an implementation/sustainment (I/S) blueprint.

Aim 2. Optimize, preliminarily evaluate, and implement Adhere.ly in community practice settings

Aim 2 of this study will use a randomized controlled OEI Hybrid trial design. The trial will include 50 community mental health providers randomized within their respective practice locations to administer CBT+Adhere.ly (n=25) vs. CBT alone (n=25) to a total of 60 treatment-seeking adult mental health patients with clinically elevated anxiety and/or depression-referred and treated by providers. Study staff will conduct pre- and post- implementation assessments remotely with providers and will facilitate web-based administration of baseline and 3-month post-baseline assessments with patients via REDCap. Treatment sessions may be audio recorded and uploaded to REDCap by providers and coded by study staff to assess provider assignment and assessment of homework. Clients will have the option to allow providers to audio-record their therapy sessions through the consent. Patient homework adherence will be assessed weekly the day of their next session using a REDCap survey, a link to which will be sent via automated text-message and/or email reminders, or by telephone after 1 day of no response.

5.2

 Audio/Video Recording	 Psychophysiological Recording
 Behavioral Interventions	 Record Review - Educational
 Behavioral Observations and Experimentations	 Record Review - Employee
 Deception	 Record Review- Medical
 Focus Groups	 Record Review - Other
 Interviews	 Specimen Collection or Analysis
 Investigational Device – Non-Significant Risk (e.g. Mobile Applications)	 Surveys and/or Questionnaires
 Psychometric Testing	 Other Social-Behavioral Procedures

Aim 1. Understand and prioritize key stakeholder goals, challenges, affordances, and constraints

Study staff will invite up to 24 adult mental health patients, 24 providers, and 24 administrators to participate in remote (i.e., video conference or telephone), ≤90-minute, screen and audio-recorded, semi-structured focus groups to inform the design of new Adhere.ly features and exercises and an I/S blueprint. Study staff will email and/or call mental health providers and administrators registered with Doxy.me—who will be asked to refer adult patients—with information about the study and an invitation to participate (see attached Letter of Support from [name] at Doxy.me). Study staff will also post recruitment flyer on Facebook and submit research study into the Institute of Translational Health Sciences (ITHS) to recruit adult patients. Study staff will schedule an appointment to obtain verbal informed consent and begin focus groups, which will include basic demographic questions, an overview and brief demonstration of Adhere.ly, and will utilize the Modified Consolidated Framework for Implementation Research (mCFIR) domains relevant to Adhere.ly features and exercises and this implementation (i.e., intervention characteristics, outer settings, inner settings, end-user characteristics, and process of implementation).^{36,37} Next, we will draw upon insights obtained from these focus groups and the literature on homework and processes-based CBT to develop a quantitative web-based survey that we will administer to 100 mental health providers, recruited via emails to providers registered with Doxy.me, to prioritize certain goals, challenges, features, and exercises.^{38,39}

Aim 2. Optimize, preliminarily evaluate, and implement Adhere.ly in community practice settings

Recruitment of providers

We will leverage research-practice partnerships established in Aim 1 to recruit 50 master's-level mental health providers and will recruit additional providers via emails to mental health providers registered with doxy.me, if needed. Providers will be contacted by study staff via telephone and/or email to inform them about the study and inquire about their interest in participating. Providers who express interest in participating in the study will be scheduled for a 60-minute, televideo-based consent and training process with study staff to discuss the study, referral procedures, audio recording sessions, and uploading recordings to REDCap. Signed informed consent from providers will be obtained by study staff via REDCap e-Consent. Afterwards providers will complete a

demographics questionnaire and the Attitudes Toward Homework Questionnaire (ATHQ).¹²

Recruitment of patients

We will recruit 60 treatment-seeking adults over 18 with clinically elevated anxiety and/or depression. Patients will be referred and by providers following their initial intake session with that provider. We will ask providers to refer 3-4 patients to maximize the likelihood of treatment completion with at least 3 patients. Providers will receive automated weekly emails with reminders to make referrals and links to a REDCap referral form. Providers will also be able to provide referral information via telephone or email if preferred. If patients express interest in the study, providers will assist them in completing the referral or obtain verbal consent to submit their referral information.

Upon receiving a referral, study staff will contact patient within one working day to provide study information, assess eligibility, obtain signed informed consent from patients via REDCap e-Consent, and assist patient in completing baseline assessments. Study staff will assess eligibility by: (1) administering a phone screen to the patient; and (2) emailing or texting patient a link through the REDCap system to a survey that will include a brief demographic questionnaire, the Generalized Anxiety Disorder-7 (GAD-7) or Patient Health Questionnaire-8 (PHQ-8).⁴⁰⁻⁴² Patients who are eligible, as indicated by a score ≥ 10 on the GAD-7 or PHQ-8, will then provide informed consent via REDCap e-Consent, and complete the remaining study baseline questionnaires.

Treatment

Providers will be randomly assigned to administer either CBT alone (n=25) or CBT+Adhere.ly (n=25). All providers will be asked to administer CBT as they usually would for each patient, either in-person or via telemedicine, with CBT+Adhere.ly providers integrating Adhere.ly into treatment with their patients. To minimize risk of CBT alone (i.e., “control”) providers being less motivated to refer cases, providers will be informed of their assignment only after their first study-eligible patient has been enrolled. Each provider will be asked to treat 3 patients over the course of 3 months. Providers will be asked to audio record their treatment sessions using either audio recorders provided by the study team, or audiorecording software on their computer, if preferred. Clients will have the option to audio record the treatment sessions through their consent. Providers will be asked to upload those recordings to REDCap either weekly or bi-weekly. Providers will receive automated weekly emails with a reminder to upload audio recordings and a link to a REDCap form for uploading recordings. This form will ask the provider to enter their name, the name of the patient being treated, the session number, and whether the session was conducted in-person or over telemedicine. Providers who have not uploaded a recording after 2 weeks will receive a follow-up phone call from study staff to provide reminders and assistance where needed.

Assessment Strategy and Measures

Trial questionnaires are shown in Table 1. Baseline and 3-month post-baseline questionnaires will be completed by patients via REDCap surveys. Study staff will email or text patients a link to the survey through the REDCap system and will be available to

remotely assist patients in completing questionnaires. As stated previously, GAD-7 and PHQ-8 will be administered to screen potential participants for eligibility criteria and will be administered prior to obtaining informed consent. The informed consent document will specify that these data will be included with participants' study data if they are eligible and agree to participate or will not be included if they are ineligible or decide not to participate.

Table 1. Assessment Measures for Trial

Domain	Informant	Measure	Time Point	
			B	3M
Demographics	Provider	Provider Demographics Questionnaire	✓	
	Patient	Patient Demographics Questionnaire		
Attitudes Toward Homework	Provider	Attitudes Toward Homework Questionnaire (ATHQ) ¹²	✓	✓
Anxiety Severity	Patient	General Anxiety Disorder-7 (GAD-7) ^{40,41}	✓	✓
Depression Severity	Patient	Patient Health Questionnaire-8 (PHQ-8) ⁴²	✓	✓
Quality of Life	Patient	Health-Related Quality of Life (CDC HRQOL-14) ⁴³	✓	✓
Therapeutic Alliance	Patient	Working Alliance Inventory- Short Revised (WAI-SR) ⁴⁴		✓
Treatment Satisfaction	Patient	Client Satisfaction Questionnaire (CSQ-8) ⁴⁵		✓

Note. B=Baseline; 3M=3-Month Follow-Up.

Provider homework use, patient homework adherence, and treatment fidelity

Patient homework adherence will be assessed weekly on the day of their next session using a REDCap survey, a link to which will be sent via automated text-message and/or email reminders, or via telephone by study staff after 1 day of no response. The first 4 items of the Homework Rating Scale II (HRS II) will be used to measure patient homework adherence.⁴⁶ Session audio recordings will be observationally coded by independent coders blinded to study aims. Provider adherence and competence in reviewing, designing, and assigning homework (i.e., homework use) will be assessed using the Homework Adherence and Competence Scale (HAACS).⁴⁷ Provider general therapeutic and CBT-specific skills to appropriately deliver CBT will be assessed by the Assessment of Core CBT Skills (ACCS).⁴⁸

Optimization

We will iteratively optimize Adhere.ly and our implementation strategies during the feasibility trial based on user data, error reports, support requests, and data from routine feedback interviews conducted by Adhere.ly, LLC. We will address unanticipated problems and opportunities encountered during implementation, remove unnecessary components and I/S strategies, and improve processes and functionality. We will develop a clear set of procedures for optimization and keep a log of all changes made for reporting purposes, consistent with the Trials of Intervention Principles outlined by Mohr and colleagues.⁴⁹

Implementation

Pre-implementation assessments will take place during Aim 1. Study staff will conduct remote, \leq 45-minute individual post-implementation interviews with \leq 10 patients and \leq 10 providers who participate in the CBT+Adhere.ly condition. Participants will be recruited via telephone by study staff and scheduled for an interview. Informed consent from providers and patients to participate in these interviews will have been obtained by study staff during the initial consent process for the trial. These interviews will use the mCFIR tool to assess perceptions about Adhere.ly's implementation and performance within each

of the mCFIR domains. To complement this evaluation of implementation processes, we will evaluate implementation outcomes with respect to Reach, Effectiveness, Adoption, Implementation, and Maintenance guided by the RE-AIM framework.^{50,51} These data will be added to the robust mCFIR data to contribute to an overall summative evaluation.

5.3

The standard of care procedures for adults with clinically elevated anxiety and/or depression is traditional CBT from provider.

5.4

There are no additional foreseeable risks to the above procedures in need of further mitigation beyond those ordinarily incurred in working with this population. Standard operational procedures of clinics specify responsibilities for handling dangers to self and others and safety planning in the event of domestic violence.

5.5

N/A

5.6

N/A

5.7

N/A

6.0 Data and Specimen Storage for Future Research

6.1

N/A

6.2

N/A

6.3

N/A

7.0 Sharing of Results with Subjects

7.1

Total scores on study questionnaires will be shared verbally by study staff with patients upon request. Total scores will also be shared with providers upon request from providers and when permission to do so is granted by patient as indicated on their informed consent form.

8.0 Study Timelines

8.1

Aim 1. Adult mental health patients, providers, and administrators will participate in one ≤90-minute focus group. Providers will be invited to complete a ≤15-minute survey.

Aim 2. Providers will participate in one \leq 60-minute consent and training process and twelve \sim 60-minute therapy sessions per study case. Study referral procedures will take an additional 5 minutes per patient. An additional 5 minutes per patient, per session will be required to upload audio recordings. Providers who participate in post-implementation interviews will spend an additional 45 minutes in the study. In all, the total amount of time spent in the study will be approximately 28 hours over the course of 9 months, only 4 hours of which will be spent engaging in study procedures beyond their everyday practice.

Patients will participate in a \leq 60-minute eligibility screening, consent, and baseline assessment process. Patients will participate in twelve \leq 60-minute therapy sessions, engage in twelve \sim 10-minute homework assignments, and spend \leq 5 minutes each week completing homework assessments. 3-month follow-up assessments will take \leq 30 minutes. Patients who participate in post-implementation interviews will spend an additional 30 minutes in the study. In all, the total amount of time spent in the study will be approximately 17 hours over the course of 6 months, only about 5 hours of which will be spent engaging in study procedures beyond the time they would have otherwise been receiving therapy from their provider.

9.0 Inclusion and Exclusion Criteria

9.1

Aim 1. English-speaking, adult (\geq 18 years old) mental health patients, providers, and administrators.

Aim 2.

Providers: English-speaking, mental health providers who have obtained at least a master's degree in social work, counseling, clinical psychology, or related field; carry active adult mental health treatment caseloads; and have a laptop, tablet, or smartphone with internet access.

Patients: English-speaking, treatment seeking adults \geq 18 years with clinically elevated anxiety and/or depression as indicated by a score \geq 10 on the GAD-7 and PHQ-8; and have a laptop, tablet, or smartphone with internet access.

9.2

Patients with self-reported (1) active psychotic symptoms (e.g., hallucinations, delusions) or (2) significant cognitive disability, based on the phone screen.

9.3

Patients will be ineligible to continue if there is a discontinuation or interruption of CBT treatment with participating provider. If a patient changes therapists to a provider enrolled in the study, they will be able to participate with the new provider but will be re-consented to confirm that they still want to participate with the new provider and will be notified that their baseline questionnaire data will be maintained to avoid the unnecessary burden of collecting those data a second time.

9.4

We will be including employees as participants.

10.0 Vulnerable Populations

10.

N/A

11.0 Local Number of Subjects

11.1

N=282

Aim 1 focus groups: n=24 patients; 24 providers; 24 administrators

Aim 1 survey: n=100 providers

Aim 2 trial: n=50 providers; 60 adult patients

12.0 Recruitment Methods

12.1

 Email	 Online/Social Media Advertisement
 Flyer	 Record Review
 Letter	 SONA
 News Advertisement	 Other

12.2

Aim 1. Study staff will email and/or call mental health providers and administrators registered with Doxy.me—who will be asked to refer adult patients—with information about the study and an invitation to participate (see attached Letter of Support from [name] at Doxy.me). Study staff will also post recruitment flyer on Facebook and submit research study into the Institute of Translational Health Sciences (ITHS) to recruit adult patients. Study staff will then schedule an appointment to obtain verbal informed consent and conduct focus groups. We will recruit 100 mental health providers registered with Doxy.me via email to complete the web-based survey.

Aim 2. Providers will be recruited by leveraging research-practice partnerships established in Aim 1 and will recruit additional providers via emails to mental health providers registered with doxy.me, if needed. Providers will be contacted by study staff via telephone and/or email to inform them about the study and inquire about their interest in participating. **Patients** will be referred and by providers following their initial intake session with that provider. We will ask providers to refer 3-4 patients to maximize the likelihood of treatment completion with at least 3 patients. Providers will receive automated weekly emails with reminders to make referrals and links to a REDCap referral form. Providers will also be able to provide referral information via telephone or email if preferred. Providers will be given informational cards with a QR code to the referral form. If patients express interest in the study, providers will assist them in completing the referral or obtain verbal consent to submit their referral information. Upon receiving a referral, study staff will contact patient within one working day to

provide study information, assess eligibility, obtain signed informed consent from patients via REDCap e-Consent, and assist patient in completing baseline assessments.

12.3

N/A

13.0 Withdrawal of Subjects

13.1

If a participating provider decides to withdraw participation from the study, patients being treated by that provider will also be withdrawn from the research without their consent and will revert to standard treatment. If a patient changes therapists to a provider enrolled in the study, they will be able to participate with the new provider but will be re-consented to confirm that they still want to participate with the new provider and will be notified that their baseline questionnaire data will be maintained to avoid the unnecessary burden of collecting those data a second time.

13.2

Subjects who withdraw will continue to receive the same standard of care from their mental health provider.

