16.0 Data Management and Confidentiality

16.1

Aim 1 Data Analysis

Focus group transcripts will be coded by trained study staff in NVivo using a hybrid inductive-deductive, consensus-based content analysis,⁵²⁻⁵⁴ and the mCFIR tool.^{36,37,55} Coders will meet regularly to ensure consistency with code definitions and resolve inconsistencies via discussion to achieve consensus. Data aggregation queries will be used to create case memos and assign ratings for mCFIR constructs. Survey data will be analyzed to describe provider goals, challenges, affordances, and constraints. We will use the Expert Recommendations for Implementing Change (ERIC) matching tool to generate a list of potential implementation strategies for refinement.^{56,57} We will synthesize qualitative and quantitative findings to prioritize new features, exercises, and I/S strategies.

Aim 2 Data Analysis

Feasibility

We will assess feasibility of the proposed trial methodology using the following benchmarks, which were informed by the sample size needed for hypothesis testing in Phase II and expert recommendations.⁵⁸⁻⁶¹

Benchmarks: 50 providers will be enrolled in months 1-2 [20/month]); 60 patients will be enrolled in months 2-6 [8/month]); 70% of providers and patients will use Adhere.ly; 70% of session recordings will be uploaded; 70% of weekly HRS II assessments will be completed; 70% of patients will be retained at 3-month follow-up.

Evaluation

The small sample size prevents any conclusions about effectiveness; however, ANCOVA will be used to preliminarily assess-between group differences in clinical outcomes while co-varying for pre-treatment scores. ANOVA will be used to compare homework use and adherence. We also will preliminarily examine relations among study variables (therapeutic alliance, satisfaction).

Implementation

Interview transcripts will be coded by trained study staff in NVivo using the mCFIR

coding scheme developed during Aim 1. Data aggregation queries will be used to create case memos and assign ratings for mCFIR constructs, which we will examine between pre- and post-implementation using a modified CFIR matrix template. We will further synthesize qualitative with quantitative (i.e., mCFIR, RE-AIM) results to confirm and/or explain summative evaluation findings.

Table 2. RE-AIM outcomes

Dimension	Results

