Reach	Number of potential providers and patients available for recruitment; percentage eligible/ineligible, invited, and enrolled; sample characteristics; reasons for ineligibility and varying levels of engagement; ambiguities regarding eligibility criteria
Effectiveness	Attrition and related patient characteristics; adverse events; satisfaction; impact
Adoption	Estimated number of settings for future trials; settings and stakeholder characteristics
Implementation	Percentage of providers and patients who use Adhere.ly; average number of exercises used by providers and patients; percentage of session recordings uploaded; percentage of weekly HRS II completed; degree of use and adherence; provider/patient time costs; patient retention; assessment time burden; completed assessments; missing items; broken/lost/stolen equipment; technical issues
Maintenance	Clinical outcomes at 3-months post-baseline

16.2

All data collected during the trial will be securely stored in a REDCap database, including informed consent/assent documents, questionnaire data, and audio recordings. Data obtained from Adhere.ly platform for the purposes of this study will include names, phone numbers, and email addresses, and usage data relating to providers practicing, assigning, and assessing exercises, and patients completing those exercises. These data will be downloaded from Adhere.ly and merged with the data in REDcap. Only IRB-approved and trained study personnel will have access to the REDCap project and access will be limited to information and modules that are required for them to complete their assigned study-related tasks. All identifiers will be marked as such in REDCap and will not be included in the final exported dataset, which will instead include assigned ID numbers.

We will use the following security measures to protect data sources:

1. all research data exported from REDCap will include ID numbers only
2. the codes that link the name of the participant and the study ID will be kept confidential in REDCap
3. computers and servers containing data will be password-protected to prohibit unauthorized access
4. online survey data collection will be accessible only by IRB approved study staff with secure logins
5. Adhere.ly includes state-of-the-art technical infrastructure—including encryption and other software, security practices, and business operational practices to ensure compliance with all major governing legislation, including HIPAA

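### Patients are removed from the research when their provider withdraws, and apparently when CBT stops; neither rule keeps the remote 3-month survey, so obtainable outcomes are lost and the 70% retention benchmark mixes removal by rule with non-response

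*Combined protocol and SAP*

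**What the plan says.** Section 13.1 covers a provider who leaves the study: "patients being treated by that provider will also be withdrawn from the research without their consent". Section 13.2 then assures continued care for those who withdraw, but says nothing about continued data collection.

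Section 9.3 covers a change in treatment: "Patients will be ineligible to continue if there is a discontinuation or interruption of CBT treatment with participating provider". Both 9.3 and 13.1 give the same single exception: "If a patient changes therapists to a provider enrolled in the study, they will be able to participate with the new provider". Such a patient is re-consented and the baseline data are kept.

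Under Assessment Strategy and Measures in Section 5.2, the baseline and 3-month questionnaires are REDCap surveys that patients complete from a link sent by study staff. Table 1 lists the GAD-7, PHQ-8 and CDC HRQOL-14 at 3 months, among other measures.

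The Feasibility part of Section 16.1 sets benchmarks described as "informed by the sample size needed for hypothesis testing in Phase II". Two of them matter here: "60 patients will be enrolled in months 2-6" and "70% of patients will be retained at 3-month follow-up". Table 2 lists "Attrition and related patient characteristics" under Effectiveness and "patient retention; assessment time burden; completed assessments" under Implementation. None of these terms is defined or split by cause or by arm.

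**The concern.** Stopping treatment, losing a provider and leaving the research are three different events. Section 13.1 explicitly turns the second into the third. The natural reading of 9.3 does the same with the first. A patient who consented and would answer a remote questionnaire is then never asked, because of someone else's decision or because therapy stopped.

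Three things are at stake.

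- **Lost outcomes.** The loss occurs after randomisation and is avoidable. It may also differ by arm: Section 5.2 has providers learn their assignment once their first eligible patient is enrolled, so a later provider withdrawal could depend on arm and take patients with it.
- **An ambiguous benchmark.** The trial disclaims effectiveness conclusions, so the feasibility figures are a main product. As collected, retention describes only a Phase II that keeps the same removal rules. It cannot show what completion would be if every enrolled patient were followed.
- **Transfers.** Section 5.1 randomises providers within practice locations, so a change of therapist can cross arms. The plan does not say in which arm such a patient is analysed.

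**Working it through.** **Inputs from the protocol.** 60 patients and 50 providers (Section 11.1); 3 patients requested per provider (Section 5.2, Treatment); 70% retention (Section 16.1). The 70% is a set target with no derivation, so there is no calculation of the plan's to reproduce. The protocol gives no rate of provider withdrawal, CBT discontinuation or survey response. Every such rate below is an assumption, shown as a range.

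**Step 1: the target.** With all enrolled patients as denominator, 0.70 × 60 = 42 retained, so 18 may be lost.

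**Step 2: completion needed among those still surveyed.** With *r* patients removed by rule, the requirement is 42/(60 − *r*).

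**Step 3: expected retention and chance of success.** With completion *p* among the rest, expected retention is *p*(60 − *r*)/60. The chance of reaching 42 is P(X ≥ 42) for X ~ Binomial(60 − *r*, *p*), treating responses as independent.

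| Removed *r* | Completion needed | Expected retention, *p* = 0.9 | Chance of ≥ 42, *p* = 0.9 | Expected retention, *p* = 0.8 | Chance of ≥ 42, *p* = 0.8 |
|---|---|---|---|---|---|
| 6 (10%) | 42/54 = 77.8% | 81% | 99.8% | 72% | 72.6% |
| 12 (20%) | 42/48 = 87.5% | 72% | 80.0% | 64% | 12.9% |
| 18 (30%) | 42/42 = 100% | 63% | 1.2% | 56% | < 0.1% |

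There is no sharp cut-off. At *p* = 0.9 the expected count first drops below 42 at 14 removals (0.9 × 46 = 41.4), and the chance of reaching 42 is still about 51%.

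**Step 4: what the removals mean in providers.** At the average implied by the totals, 60/50 = 1.2 patients per provider, removing 6, 12 or 18 patients through 13.1 alone takes 5, 10 or 15 provider withdrawals. If each withdrawing provider had the requested 3 patients, it takes 2, 4 or 6. One such provider costs 3/60 = 5 percentage points of retention.

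**Step 5: the same figure from different causes.** An observed 42 of 60 could be 18 non-responders (42/60 = 70% response among those asked). It could equally be 12 removed by rule and 6 non-responders (42/48 = 87.5%). If removed patients were instead dropped from the denominator, the second case would be reported as 87.5% retention.

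**Step 6: effect of surveying removed patients.** Take *r* = 12 and assume 50-70% of them answer: 12 × 0.5 = 6.0 to 12 × 0.7 = 8.4 more outcomes.

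- *p* = 0.9 among the rest: (43.2 + 6.0)/60 = 82% to (43.2 + 8.4)/60 = 86%, against 72%.
- *p* = 0.8 among the rest: (38.4 + 6.0)/60 = 74% to (38.4 + 8.4)/60 = 78%, against 64%.

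**The case against.** The strongest case on the other side has five parts.

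- **Only 13.1 is explicit.** Section 9.3 does not name the survey, and follow-up after removal might be described in the Manual of Procedures or the consent form, which are not in the document. This stands as a limit on 9.3: there the claim is a natural reading, not a certainty. It does not affect 13.1.
- **The rates are invented.** Removing 20% through 13.1 alone would take 10 of 50 providers at the average caseload, and the transfer exception lowers the count. Patients are also nested in providers, so independent binomial responses are a simplification. All of this stands. The figures show how sensitive the benchmark is; they are not a forecast.
- **The benchmark tests the methodology as proposed**, so counting provider withdrawal and stopped CBT as losses is legitimate. That is fair for a Phase II with identical rules. It leaves open the rate Phase II could achieve by following everyone.
- **Causes can be recovered at reporting.** Table 2 lists retention and completed assessments separately, and Section 16.3 has staff document contacts and track data collection. This could label why a patient was lost. It cannot supply a survey that was never sent.
- **The stakes are modest and the amendment is late.** The trial is not powered (Section 2.2), effectiveness is disclaimed, and at V10 some patients may already be past 3 months. This limits the gain but leaves a real one for those still in follow-up or not yet enrolled.

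**Conclusion.** The concern holds. Section 13.1 ends data collection for patients of a withdrawing provider, 9.3 most naturally does so when CBT stops, and no part of the protocol keeps the remote survey for either group. This goes beyond missing detail, because following the stated rule loses outcomes that could be obtained.

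The size depends on rates the documents do not give. Over assumed removal of 10-30% and completion of 80-90% among the rest, expected retention runs from 81% down to 56%, and the chance of reaching 42 runs from over 99% to under 0.1%. A missed benchmark could therefore reflect the rule rather than unwillingness to respond. The size and direction of any difference in loss between arms cannot be found from the documents.

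The rules should be changed. Confidence is medium, because 9.3 is open to interpretation and the removal rate is unknown.

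**What to change.** - In 9.3 and 13.1, separate stopping CBT or losing the provider from leaving data collection. Send the 3-month survey to every consented patient unless that patient withdraws consent.
- In 16.1, define retention as completed 3-month assessments divided by all enrolled patients.
- State that each patient is analysed in the arm of the provider at enrolment, including patients who change therapist.
- Report CBT discontinuation, provider withdrawal and transfers by arm, separately from survey completion.

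These changes concern data collection and reporting only; no change to clinical care is proposed.

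**Cost.** Protocol and consent wording, and possibly re-consent of current patients. Each extra survey takes at most 30 minutes (Section 8.1) and carries the existing $30 card (Section 20.2). That is at most 12 × $30 = $360 or 18 × $30 = $540, for cards already offered to all 60 patients. Response among patients who stopped treatment is likely to be lower than among the rest, and those already past 3 months cannot be recovered.
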